8.3 Trial management committee (TMC)

A trial management committee (TMC) is set up with the participation of representatives from the different centers and specialist (radiation oncologist and medical physicist). The TMC will meet annually after study initiation. All events (See primary endpoint), will be reviewed by the TMC and if the rate of reirradiation at one year is excessive defined by the sample size calculation, then the TMC can, at its discretion recommend cessation of the study or dose adjustment. Furthermore, all grade 4 and 5 toxicity deemed caused by the radiation treatment will be reviewed by the TMC.

9 Ethical aspects

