2.4 Definition of endpoint related concepts

- The duration of patient reported gastric-oesophageal toxicity is measured as the time from an increase in gastro-oesophageal symptom score to a return to baseline
- Reirradiation rate is defined as fraction of patients getting reirradiation, where the same spine levels are included in the irradiated volume
- OS is defined as time from inclusion until death from any cause
- diabetes developed during glucocorticoid treatment will be defined as two random plasma glucose measurements $\geq 11,1$ mmol/L.
- Time-in-range is defined as the percent of time glucose value is in normal range (3,9-10 mmol/L)
- Time above range is defined as the percent of time the glucose value is above normal range
- Time below range is defined as the percent of time the glucose value is below normal range
- Coefficient of variation for glucose is calculated as **(Standard Deviation / Mean) * 100**

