3.3 Sample size calculation for primary endpoint

We assume that we can decrease maximum esophageal dose from 30 Gy to 10 Gy and that this will result in a 50% decrease in risk of early esophageal toxicity.¹¹ We want to conduct a phase III trial with 1:1 randomization between standard VMAT and experimental esophageal VMAT. Prior data

indicate that the rate of early esophageal toxicity with standard VMAT is 0.6. ¹¹ If the true early esophageal toxicity rate in the esophagus sparing VMAT arm is 0.3, conventional power calculation indicates that we would need to include 62 patients in each arm, to be able to reject the null hypothesis that the toxicity rates for experimental and control arms are equal with a probability (power) of 0.9. The Type I error probability associated with the test of this null hypothesis is 0.05 and calculations are performed assuming Fisher's exact test. However, with this patient population we anticipate high rate of heterogeneity and we need to account for loss of follow-up due to patients dying early or being too frail. We increase the study size to 100 patients in each arm to account for these challenges. Patients will be stratified according to performance status and fractionation scheme.

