3.4 Ambulatory function as a co-primary endpoint

We wish to demonstrate that the improvement in esophageal toxicity does not come at a price of reduced effect of the radiation. As a prioritized secondary endpoint, we choose ambulatory function (preserved ability to walk) measured on a 4-point scale. We assume that the conventional arm follows the distribution of the SCORAD trial and test our ability to detect a difference from an assumed inferior experimental arm in terms of ambulatory function, see Table 1.⁷

If the underlying “true” distribution on ambulatory grades is as depicted in the table and we assume 66 patients per arm are evaluable, we find that 84% of simulated trials would lead to statistically significant differences detected with a Wilcoxon rank sum test for comparing the trial arms. In other words, the power of the trial is enough to detect a deterioration according to the able, which would lead to rejection of the experimental treatment.

	Conventional arm	Experimental arm
Grade 1: Ambulatory without the use of walking aids	22	11
Grade 2: Ambulatory with walking aids	44	32
Grade 3: Unable to walk	26	37
Grade 4: Absence or flicker of motor power in any muscle group	8	20

Table 1: Distribution of ambulatory function. The conventional arm follows the SCORAD trial (7).

The power of ESO-SPARE is enough to detect a difference in ambulatory function as seen in Table 1.

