9.1 Ethical considerations

The focus of this study is palliation with reduction of side effects from necessary radiation therapy for MSCC. The study participants are fragile with low life expectancy.^{2,5} In order to minimize the time, spend in hospital, we designed the study with electronical/telephone follow-up only.

All toxicology data will be collected as patient reported outcomes (PRO). All though we will not act directly the collected PRO, the patients will be encouraged to contact the department with any problems there might occur.

In order to compute a radiation plan with sparing of the esophagus for patients in the experimental arm, it might be necessary to compromise the dose delivered to the anterior part of the vertebra close to the esophagus. While we do not expect the treatment in the experimental arm to be less effective, it is one of the objectives of this study to examine this. Reirradiation rates in the two arms will be assessed continuously. The TMC can recommend cessation of the study or dose adjustments if the reirradiation rate in the experimental arm is to excessive.

There will be no extra radiation from extra scans in this study.

In order to determine the natural course of plasma-glucose during and after high-dose glucocorticoid treatment, we wish to perform a real-life study with as little intervention as possible. Therefore, we intend to use blinded glucose measurements only. For study participants 1-2 fewer glucose measurements pr. week compared to current standard is expected. Patients participating in

the study by Schultz et al received 300 mg Prednisolone daily for 10 days, which was local standard at the time.¹⁵ The guidelines have since been modified and currently recommended Prednisolone doses as well as duration of treatment is significantly lower.¹³ Because of this, we expect the incidence of glucocorticoid induced hyperglycemia and diabetes to be lower in our study population.

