We assume that we can decrease maximum esophageal dose from 30 Gy to 10 Gy and that this will result in a 50% decrease in risk of early esophageal toxicity. We want to conduct a phase III trial with 1:1 randomization between standard VMAT and experimental esophageal VMAT. Prior data (2) indicate that the rate of early esophageal toxicity with standard VMAT is 0.6. If the true early esophageal toxicity rate in the esophagus sparing VMAT arm is 0.3, conventional power calculation indicates that we would need to include 62 patients in each arm, to be able to reject the null hypothesis that the toxicity rates for experimental and control arms are equal with a probability (power) of 0.9. The Type I error probability associated with the test of this null hypothesis is 0.05 and calculations are performed assuming Fisher's exact test. However, with this patient population we anticipate high rate of heterogeneity, and we need to account for loss of follow-up due to patients dying early or being too frail. We increase the study size to 100 patients in each arm to account for these challenges. Patients will be stratified according to fractionation scheme and treating center.

Ambulatory function as a co-primary endpoint

We wish to demonstrate that the improvement in esophageal toxicity does not come at a price of reduced effect of the radiation. As a prioritized secondary endpoint, we choose ambulatory function (preserved ability to walk) measured on a 4-point scale. We assume that the conventional arm follows the distribution of the SCORAD trial and test our ability to detect a difference from an assumed inferior experimental arm in terms of ambulatory function, see Table 2.

If the underlying “true” distribution on ambulatory grades is as depicted in the table and we assume 66 patients per arm are evaluable, we find that 84% of simulated trials would lead to statistically significant differences detected with a Wilcoxon rank sum test for comparing the trial arms. In other words, the power of the trial is enough to detect a deterioration according to the able, which would lead to rejection of the experimental treatment.

The power of ESO-SPARE is enough to detect a difference in ambulatory function as seen in Table 2

	Conventional arm	Experimental arm
Grade 1: Ambulatory without the use of walking aids	22	11
Grade 2: Ambulatory with walking aids	44	32
Grade 3: Unable to walk	26	37
Grade 4: Absence or flicker of motor power in any muscle group	8	20

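### Protocol 8.3 takes the TMC's re-irradiation trigger from the sample size calculation, but no sample size calculation contains a re-irradiation rate, difference or margin, so the cited threshold does not exist

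*Protocol*

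**What the plan says.** Protocol 8.3 sets up an annual TMC review. The condition for action is "if the rate of reirradiation at one year is excessive defined by the sample size calculation"; if it is met, "then the TMC can, at its discretion recommend cessation of the study or dose adjustment".

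Protocol 9.1 states the same power again: "Reirradiation rates in the two arms will be assessed continuously", and "The TMC can recommend cessation of the study or dose adjustments if the reirradiation rate in the experimental arm is to excessive". It mentions neither a one-year time point nor the sample size calculation, and it gives no figure.

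The sample size text is in three places:

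- Protocol 3.3 works from toxicity: "the rate of early esophageal toxicity with standard VMAT is 0.6", against 0.3 in the sparing arm.
- Protocol 3.4 works from walking: "we choose ambulatory function (preserved ability to walk) measured on a 4-point scale", using the distributions in Table 1.
- The SAP section on sample size repeats both calculations ("indicate that the rate of early esophageal toxicity with standard VMAT is 0.6").

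Re-irradiation is a secondary endpoint (Protocol 2.3). Its definition in Protocol 2.4 is by patient: "Reirradiation rate is defined as fraction of patients getting reirradiation", counting courses that include the same spine levels. SAP item M analyses it by Kaplan-Meier and log-rank. The SAP analysis summary lists the number and percentage of patients at 3, 6 and 12 months from inclusion.

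**The concern.** Section 8.3 tells the reader, including an ethics committee, that the level counted as excessive has been fixed elsewhere. If it has not, the sentence describes a safeguard that has no content.

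This matters because of what the experimental arm does. Under Protocol 6.4 the esophageal limit takes priority over target coverage, and 9.1 accepts that the front of the vertebra may receive less dose. Local failure is the natural cost of that trade. Re-irradiation is the only loss-of-efficacy signal that the Protocol ties to stopping or dose adjustment during the trial. Progression is kept out of adverse event reporting (8.2), so that route would not reliably show it.

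Without a recorded level, the TMC forms its view of what is excessive after seeing rates by arm. An outside reader then cannot check why the trial continued, stopped or changed dose.

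**Working it through.** **1. Do the sample size calculations use re-irradiation at all?**

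- *Toxicity (Protocol 3.3).* Inputs: 0.6 v 0.3, alpha 0.05 (taken as two-sided; the text does not say), power 0.9, Fisher's exact test, stated 62 per arm. Exact power by full enumeration is 0.894 at 60 per arm, 0.902 at 61 and 0.910 at 62. The stated figure is reproduced to within one patient per arm.
- *Walking (Protocol 3.4).* Inputs: Table 1 percentages 22/44/26/8 v 11/32/37/20, 66 evaluable per arm, Wilcoxon rank-sum test, stated power 84%. Simulation (6,000 trials, two-sided 5%) gives 82%, within two points.

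Both results are accounted for by toxicity and walking inputs alone. Protocol 3.2 and 3.6 add only accrual and compliance rules. The SAP adds no input. No redaction or missing figure in these sections could hold the number.

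**2. Could a threshold be derived from the trial size?** One natural reading is the rate that 100 per arm could detect. With control rate p1, sparing-arm rate p2 and their mean p̄:

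n = [1.96·√(2p̄(1−p̄)) + 0.842·√(p1(1−p1) + p2(1−p2))]² / (p2−p1)²

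For p1 = 0.10 and p2 = 0.25: [1.96·√0.28875 + 0.842·√0.2775]² / 0.0225 ≈ 99.5. At 80% power and two-sided 5%, the detectable sparing-arm rate with 100 per arm is:

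| Assumed control rate | Detectable rate |
|---|---|
| 5% | 17.5% |
| 10% | 25% |
| 15% | 32% |
| 20% | 38% |

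The answer depends on a control rate, and on a choice of power for this endpoint, that the documents do not supply. These figures illustrate the gap; they are not a proposed threshold.

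**3. How precise would an early look be?** The half-width of the 95% interval for a difference, with both arms at rate p, is 1.96·√(2p(1−p)/n). For p = 0.10 and n = 50: 1.96·√0.0036 = 11.8 points.

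| Assumed rate | 50 per arm | 100 per arm |
|---|---|---|
| 5% | 8.5 points | 6.0 points |
| 10% | 11.8 points | 8.3 points |
| 20% | 15.7 points | 11.1 points |

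As an example only, take a guide of 10 points at 50 per arm (five patients). By exact binomial it is reached in 7% of looks at 10% v 10%, 55% at 10% v 20%, and 92% at 10% v 30%. The rates and the 50 per arm are assumptions.

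**4. Which rate should the TMC see?** Protocol 2.4 asks for a fraction of patients, so those who die without re-irradiation stay in the denominator. Protocol 1.1 puts median survival in MSCC below 6 months. SAP item M does not say how deaths are handled. Suppose they are censored, with constant hazards: re-irradiation h = 0.02 per month (assumed), death d = ln 2/5 = 0.139 per month (assumed 5-month median). At 12 months:

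- Kaplan-Meier with deaths censored: 1 − exp(−0.02·12) = 21%.
- Cumulative incidence with death competing: h/(h+d)·[1 − exp(−12(h+d))] = 0.126 × 0.851 = 11%.

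With a 6-month median (d = 0.116) the pair is 21% v 12%. For h = 0.01 and 0.04 with the 5-month median the pairs are 11% v 6% and 38% v 20%. The gap is smaller early on: at 3 months, with h = 0.02 and the 5-month median, it is 5.8% v 4.8%.

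**The case against.** The strongest reply is that nothing operational depends on the faulty phrase. The TMC acts at its discretion. Section 9.1 gives it the same power, with both arms watched continuously, and does not refer to the sample size calculation. Deleting the phrase would leave its authority unchanged. That stands, and it limits the point to transparency.

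A second reply is that loss of efficacy is mainly guarded by the walking co-primary endpoint: under Protocol 3.4, a deterioration like that in Table 1 would lead to rejection of the sparing technique. That also stands, but it operates at the final analysis, on walking at nine weeks (SAP). It does not guide a decision during accrual.

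A third reply is that the remedy comes late. The SAP ends inclusion on April 30, 2024, or at 200 patients if sooner. Since 9.1 has both arms assessed continuously, rates by arm may already have been seen. This is fair, and it is why the fix has a disclosure route.

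Four stronger readings are tempting, and the documents do not support them:

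- *The one-year condition delays detection.* Section 9.1 allows review at any time.
- *A formal stopping boundary is broken, with an effect on type I error.* The review is advisory and no boundary is specified.
- *The toxicity or walking effect was meant to be carried over as the re-irradiation threshold.* No text says so, and a hoped-for toxicity reduction is not a tolerable excess of re-irradiation.
- *The sentence was carried over from another trial.* The preceding words in 8.3 do point to primary-endpoint events although re-irradiation is secondary, but the documents do not show where the wording came from.

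**Conclusion.** The point holds in a limited form. Section 8.3 says a threshold is defined, and it is not: neither document gives a re-irradiation rate, difference or margin. This rests on the text and on both sample size figures being explained without re-irradiation; it needs no assumed rate.

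The consequence is the loss of a checkable criterion for the only interim signal of lost efficacy. It does not bear on the validity of either co-primary analysis, and the TMC remains free to act.

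The related reporting point is conditional. If item M censors deaths, the 12-month estimate would be roughly double the fraction of patients re-irradiated under the hazards assumed above. The overstatement would be smaller if survival in the trial is longer than Protocol 1.1 suggests, as it may be, since patients with epidural ingrowth or nerve root compression are also eligible.

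It should be corrected, because the statement is wrong as written and the correction is cheap.

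**What to change.** **Protocol 8.3.** Remove the reference to the sample size calculation. In its place, have the TMC record the between-arm excess in same-site re-irradiation that it would regard as excessive, as a non-binding guide, with the decision left to its discretion. If rates by arm have been seen or accrual has closed, do not set a level in retrospect. Disclose in the trial report the criterion actually used, or that none was set.

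**TMC tables and final report.** Give cumulative incidence of same-site re-irradiation by arm at 3, 6 and 12 months from inclusion, with death as a competing event. State openly that this changes the Kaplan-Meier estimate in SAP item M. The log-rank comparison can stay.

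**Cost.** One sentence in the Protocol, one in the SAP, and a short table per review. The data are already registered: re-irradiation under Protocol section 4, further radiotherapy courses and survival under 5.5. The downside is that early looks can flag only a large excess, as step 3 of the working shows, so the guide should be described as such.

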2.3 Secondary endpoints

- Duration of gastro-oesophageal toxicity
- Reirradiation rate
- Preserved physical function measured by EORTC QLQ C30, see Appendix C.
- Changes in Quality of life (QoL) measured with EQ-5D-5L and EORTC QTQ C30
- Change in weight
- Pain reduction (MTS site) from baseline evaluated by “Numeric Pain Rating Scale (NPRS)”, see Appendix D.
- Change in analgesic consumption
- Overall survival (OS)
- Incidence of glucocorticoid induces diabetes
- Incidence of glucocorticoid induced diabetes treated with insulin
- Number of patients with normalized blood-glucose values on day 28 after start of treatment
- Incidence of hospital contacts requiring regulation of hyperglycemia
- Incidence of hospital admissions due to new-onset diabetes
- Time in range
- Time above range
- Time below range
- Mean glucose
- Standard deviation
- Coefficient of variation

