8.1 Adverse events (AE)

An adverse event (AE) is defined as any untoward medical occurrence in a patient or clinical investigation subject who has received radiation therapy for MCSS. This does not necessarily have a causal relationship with the treatment. An AE can therefore be any unfavourable and unintended symptom, (including an abnormal laboratory finding), or disease temporarily without any association with radiation therapy for MCSS. The AEs that will be reported are based upon organs at risks that most likely will be affected from radiation therapy for MCSS.

All adverse events will be graded according to the PRO-CTCAE scale and will be reported on the appropriate CRF-form.

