8.2 Serious adverse events

A serious adverse event (SAE) in human trials is defined as any untoward medical occurrence that, at any dose, results in death or is life-threatening, is disabling, requires hospitalization (whether initial or prolonged and does not include planned hospitalization) or requires intervention to prevent permanent impairment/damage. In ESO-SPARE SAEs are only registered within the nine weeks study period unless the SAE started within the 9 weeks study period but is not settled after the expiration

of the nine-weeks study period. All SAEs must be registered by the local investigator on the appropriate CRF and must be followed until they are fully settled.

Progression or deteriorating of malignancy during the study (including new metastatic lesions or death due to progression), will be part of the efficacy assessment and should NOT be reported as an AE/SAE. Symptoms clearly associated with malignancy or with concomitant or sequential systemic treatment, e.g. chemotherapy, during the study should NOT be reported as AE / SAE unless they are:

- Newly emerged (i.e. not present at baseline) and correlation with the underlying malignancy or systemic treatments are unclear.
- If there is any uncertainty as to whether an exacerbation of the subject's condition is due to the cancer disease or due to an AE, it must be reported as an AE or an SAE depending on the situation.

The local Investigator (together with the treating physician) must determine the relationship between the radiation treatment and the occurrence of a SAE as not suspected or suspected as defined below:

Not suspected:	A causal relationship of the radiation treatment is unlikely or remote, or other medications, therapeutic interventions, or underlying conditions provide enough explanation for the observed event.
Suspected:	There is a reasonable possibility that the radiation treatment caused the adverse event. 'Reasonable possibility' means there is evidence to suggest a causal relationship between the radiation treatment and the adverse event.

Furthermore, the local investigator (together with the treating physician) must determine whether a suspected serious adverse event is expected, or unexpected as defined below:

Expected:	If the treating physician/local investigator recognize the suspected SAE as an event reported in the literature and/or known from the clinical experience, this adverse event should be considered as expected.

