Unexpected:	If the treating physician/local investigator do not recognize the suspected SAE as an event reported in the literature and/or known from the clinical experience, this event should be considered as unexpected.

The assessment of an SAE should be based upon organs at risks that most likely will be affected from the radiation. Any suspected, unexpected SAE must be reported by the local investigator to the sponsor within one working day (after being aware of the incident). The sponsor can choose to change the registration of a suspected unexpected SAE to a suspected expected SAE after an audit of the case. The sponsor will inform the Ethical Committees of all relevant information about unexpected SAE, suspected to be related to the radiation treatment, that are fatal or life-threatening as soon as possible, and in any case no later than seven days after knowledge of such a case. Relevant follow-up information for these cases will subsequently be submitted within an additional eight days.

Once a year throughout the clinical trial, the sponsor will provide an updated safety report highlighting SAE to the Ethics Committee. For events not reported in the CTCAE version 5.0, the investigator will use the grade or adjectives reported in the following:

Grade 1 Mild does not interfere with patient's usual function

Grade 2 Moderate Interferes to some extent with patient's usual function

Grade 3 Severe, Interferes significantly with patient's usual function

Grade 4 Life-threatening, results in a threat to life or in an incapacitating disability

Grade 5 Death

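### GLUC-DIAB reduces glucose checks, but no rule sends a serious hyperglycaemic event to the TMC, or promptly to the sponsor

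*Protocol*

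**What the plan says.** **Monitoring.** Protocol section 7 takes GLUC-DIAB participants off standard glucose measurement. They wear a sensor whose readings neither they nor the investigators can see, and are told to contact the PI if they have symptoms. Section 4.1 has the data read after the second sensor is removed; for quality assurance, the first sensor is also read in the first 5 participants. Section 9.1 expects 1-2 fewer checks a week than standard.

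**Adverse events.** Section 8.1 sets the scope: "The AEs that will be reported are based upon organs at risks that most likely will be affected from radiation therapy for MCSS". Section 8.2 says of SAEs: "The assessment of an SAE should be based upon organs at risks that most likely will be affected from the radiation". Causality is judged against radiation only. An SAE is not suspected if a radiation cause is unlikely or remote, "or other medications, therapeutic interventions, or underlying conditions provide enough explanation for the observed event".

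**Routes upward.** Section 8.2: "Any suspected, unexpected SAE must be reported by the local investigator to the sponsor within one working day". The seven-day report to the Ethical Committees is for unexpected SAEs that are suspected to be radiation-related and are fatal or life-threatening. Also in 8.2: "Once a year throughout the clinical trial, the sponsor will provide an updated safety report highlighting SAE to the Ethics Committee".

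**TMC.** Section 8.3 has the TMC meet annually and review primary-endpoint events and the reirradiation rate. It adds: "Furthermore, all grade 4 and 5 toxicity deemed caused by the radiation treatment will be reviewed by the TMC".

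**Glucose outcomes.** Section 2.3 lists "Incidence of hospital admissions due to new-onset diabetes" as a secondary endpoint. Section 3.2 leaves the timing of secondary analyses to the study group.

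**The concern.** The study changes two things that could affect safety: the radiotherapy plan and, in GLUC-DIAB, the glucose monitoring. For the first, sections 8.3 and 9.1 provide continuous assessment of reirradiation and a committee that can recommend stopping. For the second, no body, trigger or deadline is named above the level of the PI and the treating physician.

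The checks withdrawn carry action thresholds. Under Table 5 (Herlev), two values above 11 mmol/L lead to referral to the diabetes team. Under Table 6 (Rigshospitalet), glucose is measured twice weekly in all patients, with steps at 15, 20 and 25 mmol/L. Without those checks, detection rests largely on symptoms, and section 4.2 concedes that these overlap with those of end-stage cancer.

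At stake is whether a serious event under reduced monitoring prompts anyone with study-level oversight to consider restoring checks or pausing GLUC-DIAB. As written, that depends on discretion.

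**Working it through.** There is no planned figure to reproduce. The check follows one event through the rules: a GLUC-DIAB participant is admitted with severe hyperglycaemia that the local investigator attributes to glucocorticoid.

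| Rule | Condition | Result |
|---|---|---|
| SAE registration (8.2) | Any SAE, including hospitalisation | Registered on the CRF; no deadline stated |
| Local causality assessment (8.2) | Relation to radiation | Made, but not suspected, because medication explains the event |
| Expectedness (8.2) | Asked only of suspected SAEs | Not reached |
| Sponsor, one working day (8.2) | Suspected and unexpected | Not triggered |
| Ethical Committees, seven days (8.2) | Unexpected, radiation-related, fatal or life-threatening | Not triggered |
| TMC (8.3) | Primary-endpoint event, reirradiation, or radiation-caused grade 4-5 toxicity | Not triggered |
| Yearly Ethics Committee report (8.2) | SAEs | Covered |
| PI contact or alert (4.2, 9.1) | Patient calls, or fills in the other-symptoms field | May reach the PI; no onward step stated |

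No step asks whether fewer glucose checks contributed.

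**Checks lost.** The rate is 1-2 a week (9.1). The documents do not say how long standard checks last. Over an assumed 1 to 4 weeks the loss is 1 × 1 = 1 to 2 × 1 = 2 checks at the short end, and 1 × 4 = 4 to 2 × 4 = 8 at the long end. High-dose steroid may stop after 5 days (1.3), so the short end is plausible. Table 5 prescribes no checks at HbA1c of 39 mmol/mol or below, so those Herlev patients lose none.

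**Nearest rate in the documents.** Section 1.3 reports an earlier cohort of 131, with 16 treated with insulin (taken as one cohort): 16/131 = 12.2%, exact 95% CI 7.1% to 19.1%. Applied to 150 this gives 150 × 0.122 = 18; half the rate gives 9. These are insulin treatments, not SAEs. They arose at 300 mg of prednisolone daily for 10 days, and section 9.1 expects fewer cases at current doses.

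**Serious events.** No rate is given, so the following rates are assumed. Expected number = 150p; chance of at least one = 1 − (1 − p)^150.

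- p = 0.5%: 0.75 expected; 1 − 0.995^150 = 53%
- p = 1%: 1.5 expected; 1 − 0.99^150 = 78%
- p = 2%: 3 expected; 1 − 0.98^150 = 95%

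These count all serious hyperglycaemic events, including those that standard checks would not prevent. They show only that at least one event is plausible.

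**Interval between yearly reports.** With even accrual over three years (assumed), 150/3 = 50 participants enter each year.

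**The case against.** The strongest reply is that such events are far from invisible. Section 8.2 requires every SAE to be registered and followed until settled, and the local investigator and treating physician must assess it. The Ethics Committee gets a yearly report. Section 4.2 sends symptom contacts and other-symptom entries to the PI, and physicians can measure glucose whenever they judge it necessary. Section 11 gives the PI overall responsibility. GLUC-DIAB is observational, the steroid is standard care, the loss of checks is modest, and tying expedited reporting to the randomised intervention is a recognisable choice.

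All of that stands, and it limits the point. It would be wrong to infer that the event prompts no required review: local assessment and the yearly report are both required. What is missing is TMC review and a prompt route to the sponsor. The SAP title page lists PI and sponsor as separate roles, and no rule links what the PI learns to either body.

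A reader might also infer that such an event need not be reported at all, because 8.2 says that symptoms clearly associated with the malignancy "or with concomitant or sequential systemic treatment, e.g. chemotherapy, during the study should NOT be reported as AE / SAE". The documents do not support extending this to steroids. Section 4.4 lists corticosteroids under supplemental treatment, while section 4.5 uses systemic therapy for antineoplastic drugs. The example in 8.2 is chemotherapy, and where the link to systemic treatment is unclear, newly emerged symptoms remain reportable.

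**Conclusion.** The gap is real but narrow. A steroid-explained hyperglycaemic SAE in GLUC-DIAB is registered, locally assessed and reported yearly. Because causality is judged only against radiation, it triggers neither the one-working-day report to the sponsor nor TMC review, and nobody is required to consider the reduced monitoring. This follows from the text and does not depend on any assumed rate.

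The excess risk is unknown. The documents give no serious-event rate and GLUC-DIAB has no comparator, so neither the plan nor later case review can show that reduced monitoring is unsafe; review could only prompt caution. Even 3 events in 150 would have an exact 95% CI of 0.4% to 5.7%.

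Nor should expectedness be counted as a second failure under the present rules, since it is asked only of suspected SAEs. It matters for the remedy: if causality alone were widened, hyperglycaemia already known from the literature could be called expected and still not be expedited. This is a cheap improvement to patient safety, not a flaw in the randomised comparison.

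**What to change.** In section 8.2, add:

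> For GLUC-DIAB participants, each SAE is also assessed for relation to hyperglycaemia or to the reduced glucose monitoring; the limitation to radiation organs at risk does not apply to this assessment. Any hyperglycaemia-related hospital admission, life-threatening event or death is reported to the sponsor within one working day of awareness, whatever its radiation causality or expectedness.

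In section 8.3, add:

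> The sponsor forwards these events to the TMC, which reviews them ad hoc between annual meetings, with advice from the local diabetes team where needed, and may recommend pausing GLUC-DIAB or restoring standard glucose checks.

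The cost is a few ad hoc reviews by an existing committee: 0.75 to 3 expected at assumed rates of 0.5% to 2%, and 150 × 0.05 = 7.5 at 5%. The diabetes advice is there because the specialists named for the TMC are a radiation oncologist and a medical physicist. Blinding of the sensor and the GLUC-DIAB endpoints are unaffected unless the TMC recommends a change.
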